### 2. The Need for Smoking Cessation Support for Nondaily Smokers

Nondaily smokers are motivated to quit smoking. Indeed, epidemiological evidence demonstrates that compared to daily smokers, nondaily smokers have greater current intentions to quit smoking, and more recent and planned cessation efforts than daily smokers. The fact that nondaily smokers regularly abstain from smoking from day-to-day suggests that they should have relatively little trouble quitting, but recent evidence demonstrates that most nondaily smokers (up to 82%) fail in their quit attempts. Together, the high motivation to quit coupled with a high failure rate demonstrate the need for smoking cessation support for nondaily smokers.

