## **Control Condition #2: Treatment as Usual (TAU)**

Participants in the treatment as usual (TAU) condition will be asked to make a naturalistic quit attempt, using any methods they feel might help them. To time-match the onboarding experience of SiS and QG participants, study staff will use an onboarding script to lead TAU participants through the NCI booklet “Clearing the Air”, which encourages activities in the same order as implemented in the SiS behavioral challenges (i.e., reflecting on reasons to quit, informing about benefits of quitting, logging smoking and its triggers, formulating strategies for dealing with triggers). Additionally, “Clearing the Air” provides information on smoking cessation support resources, such as counseling and pharmacological approaches.

At the end of treatment, participants complete an online survey via REDCap. This is our primary study endpoint (see Specific Aims). Participants complete two more online surveys via REDCap, occurring 12 and 24 weeks post-quit, for secondary aims.

Table 1 specifies which data are collected at which time points. Please see attached for specific descriptions of each of these measures.

Table 1. Data Collection Instruments per Time Point

Type of Measure Specific Measure	Timing of Assessment				
	BL	Wk 2	Wk 6	Wk 12	Wk 24
Primary Outcome					
Smoking Self-Efficacy Questionnaire (SEQ-12)	X	X	X	X	X
Secondary outcomes					
Smoking status	X	X	X	X	X
Recent cigarette use	X	X	X	X	X
Client Satisfaction Questionnaire (CSQ-8)			X		
Time spent applying content			X	X	X
Use of smoking cessation strategies			X		
Perceived impact of SiS/QG/TAU on quitting			X		
Appreciation Scale (AS)			X		
(SiS/QG only) Actual app usage - continuously recorded	X	X	X	X	X
(SiS/QG only) Self-reported app usage: weeks -1 to 2		X			
(SiS/QG only) Self-reported app usage: weeks 3 to 6			X		
(SiS/QG only) App likeability & satisfaction			X		
(SiS/QG only) System Usability Scale (SUS)			X		
Other outcomes to be explored in mediational analyses					
Emotional well-being					
PANAS Positive And Negative Affect Schedule (PANAS)	X	X	X	X	X
Happiness single-item measures	X	X	X	X	X
Satisfaction With Life Scale (SWLS)	X	X	X	X	X
Subjective Happiness Scale (SHS)	X	X	X	X	X
Perceived Stress Scale (PSS10)	X	X	X	X	X
Desire to smoke					
Brief Questionnaire of Smoking Urges (QSU)	X	X	X	X	X
Thought action repertoire					
Modified Twenty Statement Test (mTST) - Baseline	X				

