- 2.2. To test for differences between randomized groups for outcomes that are only assessed at end of treatment (Aims 2c – 2l), for each outcome, we will use a fixed effects model, where GROUP is the only predictor, and score at end of treatment is the dependent variable. Histograms will be used to guide selection of the most appropriate distribution. We anticipate that we will use the normal distribution for the CSQ-8 (Aim 2c), use of strategies (Aim 2e), perceived impact (Aim 2f), the AS (Aim 2g), actual app usage (Aim 2h), self-reported app usage (Aim 2i), likeability of the app (Aim 2j), satisfaction with the app (Aim 2k), and the SUS (Aim 2l), as implemented via the PROC MIXED procedure in SAS. We anticipate that we will use the Poisson distribution for time spent applying content (Aim 2d), as implemented via the PROC GENMOD procedure in SAS. If the GROUP effect is statistically significant ( $p<0.05$ ), we will conduct pair-wise follow-up tests that compare the three possible pairwise comparisons (i.e., SiS vs. QG, SiS vs. TAU, and QG vs. TAU). These follow-up analyses will not be necessary for secondary outcomes that are only assessed for the SiS and QG conditions (i.e., Aims 2j-2l).
3. Exploratory mediational models (Aim 3): We will use mediational modeling, using the product-of-coefficients approach and a fully lagged model to test if hypothesized within-person changes (see Figure 1) occur, and if they are linked to subsequent abstinence. The independent variable will be randomized group assignment (i.e., SiS vs. TAU), and the outcome variable will be self-reported 30-day point prevalence abstinence as measured at 6-month follow-up). The mediators will be our theorized mechanisms of change, as listed in the Aim 3 (i.e., self-efficacy, emotional well-being, desire to smoke, breadth of thought-action-repertoire, processing of processing of self-relevant health information.). Baseline values on these constructs will be included in the model to control for individual differences

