on these measures. The mediator will be scale scores observed at mid-treatment, at the 2-week assessment, which marks the end of the cessation phase. We will use multiple mediation to determine the relative importance of each mechanism, and moderated multiple mediation to identify differences in mechanisms across subgroups (e.g., males vs. females, young adult vs. older adults), similarly to our approach in delineating mechanisms of behavior change in Alcoholics Anonymous.

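### Aim 3 mediation: Week 2 mediator scores are related to 6-month abstinence with no smoking term, so a mediator-to-abstinence path cannot be told apart from early lapse (minor; exploratory aim only)

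*Combined protocol and SAP*

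**What the plan says.** All references are to the combined protocol and SAP. Section II, Aim 3, labelled exploratory, sets out to explain how the app conferred benefit or, if it did not, whether the treatment failed to move the mechanisms or the mechanisms failed to move the outcome.

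Section VI, Analytic Plan item 3, uses product-of-coefficients mediation in a lagged model:
- Exposure: "The independent variable will be randomized group assignment (i.e., SiS vs. TAU".
- Mediator: "The mediator will be scale scores observed at mid-treatment, at the 2-week assessment", a time point "which marks the end of the cessation phase".
- Outcome: "the outcome variable will be self-reported 30-day point prevalence abstinence as measured at 6-month follow-up".
- Covariates: "Baseline values on these constructs will be included in the model to control for individual differences". No others are named.
- Use: to see whether the mechanisms change and "if they are linked to subsequent abstinence", then to rank them against one another by multiple mediation.

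Table 1 (section V) marks smoking status and "Recent cigarette use" for collection at baseline and Week 2. Aim 2b analyses Week 2 past-week cigarettes as an outcome. Neither measure appears in item 3. Section I.2 states that "most nondaily smokers (up to 82%) fail in their quit attempts", without saying when they fail.

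**The concern.** Week 2 falls about 14 days after the quit day. A participant who has already smoked may report less confidence, stronger urges or weaker commitment because of that lapse, and the lapse itself makes abstinence at 6 months less likely. Early smoking is then a common cause of the mediator score and the outcome. Adjusting for the baseline score does not remove it, because the lapse happens after baseline. The lag from Week 2 to Month 6 does not remove it either, because the lapse comes before the lag begins.

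The stake is how Aim 3 is interpreted. A scale that merely registers whether someone has lapsed could look like a mechanism, and the scale most sensitive to lapse could rank highest. Self-efficacy is both a mediator here and the primary outcome, and section VI justifies it as primary outcome by an earlier mediation result. A spurious path from self-efficacy to abstinence would wrongly support the same choice in later trials.

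**Working it through.** **Sample size.** The mediation analysis has no figure of its own, so the check uses the 64 per group of section VI. Assuming two-sided alpha 0.05 and 80% power (neither sidedness nor target power is stated), the normal formula gives 2 × (1.960 + 0.842)² / 0.50² = 62.8, so 63. The exact t-test gives power 0.795 at 63 and 0.801 at 64, so the plan's 64 reproduces. Enrolling 75 at 85% retention gives 63.75. That retention applies to end of treatment; none is stated for 6 months.

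**Model checked.** SiS vs TAU, 64 per arm:
- Mediator equation (linear): Week 2 score on group and baseline score. The group coefficient is a.
- Outcome equation (logistic): 6-month abstinence on group, baseline score and Week 2 score. The score coefficient is b.
- Indirect effect: ab, with standard error √(a²·SE(b)² + b²·SE(a)²) (Sobel). The plan does not name the test, but it cites papers on asymptotic intervals and standard errors for indirect effects.

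**Data with true b = 0.** Week 2 score = 0.5 × baseline − shift × lapse + error of variance 0.75. Abstinence depends on lapse only. Every lapse rate, shift and abstinence rate is an assumption. There were 2,000 trials per row, and limiting values come from a sample of 200,000.

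| Lapse TAU / SiS | Shift | Abstinence without / with lapse | b | ab | False b | False Sobel | False joint (a and b) | False b, lapse in model |
|---|---|---|---|---|---|---|---|---|
| 50% / 50% | 0.8 | 45% / 15% | 0.32 | 0.002 | 33% | 0.1% | 1.2% | 4.8% |
| 60% / 40% | 0.5 | 40% / 20% | 0.14 | 0.015 | 9% | 0% | 1.0% | 5.2% |
| 60% / 40% | 0.8 | 45% / 15% | 0.31 | 0.050 | 31% | 0.6% | 5.0% | 4.3% |
| 70% / 50% | 0.8 | 45% / 15% | 0.32 | 0.052 | 34% | 0.5% | 5.2% | 4.7% |
| 70% / 40% | 1.0 | 50% / 10% | 0.48 | 0.143 | 62% | 7.0% | 24.2% | 4.8% |
| 30% / 20% | 0.5 | 40% / 20% | 0.09 | 0.005 | 8% | 0% | 0.4% | 5.6% |
| 60% / 40% | 0 | 45% / 15% | 0.00 | 0.000 | 6% | 0% | 0.4% | 4.2% |

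In the third row, a = 0.8 × (0.60 − 0.40) = 0.16 and ab = 0.16 × 0.31 = 0.050, although the true b is zero. The first row shows that the false b path does not need lapse to differ between arms. The last row shows that there is no bias if lapse leaves the score unchanged.

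A second set assumed lapse of 65% in TAU and 40-50% in SiS, with abstinence of 35-40% without and 8-10% with early lapse. A shift of 0.8 gave b of 0.34-0.41 (odds ratio e^0.34 = 1.40 to e^0.41 = 1.51), falsely significant in 28-39% of trials. A shift of 0.5 gave b of 0.25 and 16%. With lapse in the model the rates were 4-6%. This set is the source of the rough 15-40% range; the table widens it to 8-62%.

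**Reverse order.** Now let the score prevent lapse. The app raises the score by 0.5, each unit lowers the log-odds of lapse by 1.0, and abstinence is 45% without and 15% with lapse. Mediation is now real. Without lapse in the model, b = 0.305 and ab = 0.499 × 0.305 = 0.152. With it, b = 0.005 and ab = 0.425 × 0.005 = 0.002. The pattern matches the confounded case.

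**The case against.** Four counter-arguments carry weight.

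- **The planned test.** A reader might infer that the analysis would declare a false mediator in about a third of trials. The documents do not support that. They specify product of coefficients, for which the Sobel test falsely rejected in 0-7% of trials and the joint test in 0.4-24%. What survives is the b path, because Aim 3 also asks whether mechanisms affect outcome.
- **Causal order.** A reader might infer that early smoking is simply a confounder to be adjusted away. The protocol's own theory (sections I.4 and V, conceptual model) has confidence and lower craving helping people not to smoke, which would include the first two weeks. Early smoking could then lie on the causal path, and adjustment would erase a genuine effect. Nor does past-week smoking clearly precede every rating: the affect scale and one happiness item cover the past week, and the quoted stress items cover the last month. This argument stands in full.
- **Frequency of lapse.** The 82% figure is an upper figure without timing. It makes early lapse likely but does not show that most participants have lapsed by Week 2.
- **Status.** Aim 3 is labelled exploratory, Week 2 is given a rationale, and the mediator does precede the outcome. This limits the severity but does not make the b path interpretable.

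**Conclusion.** The point holds as a minor one. As written, Aim 3 cannot separate a mechanism that drives abstinence from a score that records early lapse. If early lapse shifts the scores and the scores have no effect of their own, the b path is falsely significant in roughly 15-40% of trials at 64 per arm under middle assumptions, and in 8-62% over all the assumptions tried, against a nominal 5%. A false significant Sobel test is much rarer, at 0-7%.

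These sizes rest on assumed lapse rates, shifts and abstinence rates, because the documents supply none. The effect on the ranking of mechanisms is inferred from b growing with the shift; it was not simulated with several mediators.

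The documents do not support concluding that a path which disappears on adjustment is false, since both causal orders give that result. Nor do they support any doubt about the primary or secondary analyses, which do not use this model.

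**What to change.** In section VI, Analytic Plan item 3:

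1. Add baseline recent cigarette use as a covariate in every mediation model. It precedes randomization and is already collected.
2. Prespecify each model both without and with Week 2 smoking, and report both. State the variable and the equations it enters; the b path depends on the outcome equation. Past-week cigarettes miss a lapse confined to the first week, so smoking status or any smoking since the quit day is preferable if the survey items allow it. Thirty-day abstinence cannot serve at Week 2, because only about 14 days have passed since the quit day.
3. State that the order of mediator and smoking within weeks 0-2 cannot be identified. Describe a path that vanishes on adjustment as not distinguishable from early lapse, neither proven nor refuted.
4. Do not make a mechanism claim conditional on the adjusted model.

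The cost is a few sentences, one or two model terms and a second set of estimates, with no new data. Intervals will be slightly wider and mechanism claims more hedged.

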## VII. RISKS AND DISCOMFORTS

Potential Risks: Participation will last 6 months, where surveys will be administered at enrollment, 2-week, 6-week, 3-month, and 6-month follow-up. Participants will use the provided smoking cessation support materials for a strongly encouraged period of 7 weeks (1 week before, 6 weeks following the quit attempt), and optional continued use thereafter. As such, the potential risks in the study are considered minimal and include (1) potential discomfort related to completing questionnaires about potentially sensitive information such as smoking, (2) potential breach of confidentiality and/or privacy, and (3) potential discomfort in quitting smoking (i.e., withdrawal symptoms, craving, etc.).

Protection Against Risks: For the possibility of subjective discomfort from answering questions, any distress will be minimized by assuring participants that they can refuse to answer any question that they do not feel comfortable addressing and that they may withdraw from the study at any time without penalty. To protect against breach of confidentiality, we will assign a numeric study ID to each participant, which will be the primary identifier by which this person's progress through the trial will be reviewed. The database linking names and study identification numbers will be kept in REDCap, where staff access to this information can be monitored and is password protected. Only study staff will have access to this database. All staff are or will be fully trained in relevant ethical principles and procedures, including confidentiality. All assessment and treatment procedures will be closely supervised by the PI. All data will be captured electronically. For surveys and data entry by study staff, we will be using Partners implementation of REDCap (Research Electronic Data Capture) <https://redcap.partners.org>, which is a secure, web-based application designed to support data capture for research studies, and which is fully compliant with HIPAA-Security guidelines. The data generated by using our SiS app (i.e., app usage data) will be kept on secure servers behind a firewall within the MGB network. The app will be hosted by secure ERIS/Partners servers. All data collected through the app will be transmitted using Transport Layer Security (TLS) encryption to prevent eavesdropping and tampering information while it is in the transmission pipeline. All data for all participants will be kept strictly confidential, except as mandated by law. Regarding the potential discomfort in quitting smoking, participants will receive information about how to alleviate cravings as part of their study participation. Given that study participants are nondaily smokers, who regularly abstain from smoking for several days, these discomforts are expected to be minimal.

## VIII. POTENTIAL BENEFITS

Potential Benefits: All participants will receive smoking cessation support as part of their study participation. Consequently, participants in this study may quit smoking as a result of their participation, which would have a positive impact on their health. Furthermore, study

participation will provide generalizable knowledge about the process of smoking cessation in nondaily smokers, which can be used to guide the development of further treatments to support smoking cessation in this growing population of smokers.

## **IX. MONITORING AND QUALITY ASSURANCE**

Oversight of internal monitoring of the participants' safety will be conducted by the PI, [name]. [name] will also participate in the development and administration of the plan. The PI will meet weekly with study staff on the project, at which time she will evaluate the progress of the trial, review data quality, recruitment, and study retention, and examine other factors that may affect outcome. She will review the rates of adverse events to determine any changes in participant risk and will consult with Co-I [name] and named consultants on the grant (Drs. [name] (Brown University), [name] (MGH), as necessary. (Consultants will not have access to identifiable information, nor data other than in summary form, as prepared by study staff.) A brief report will be generated annually for the study record and forwarded to Massachusetts General Hospital's Institutional Review Board. The Investigators will be available to meet outside of the weekly meetings, if necessary, due to concerns regarding a particular participant or any problems that may arise for participants. If necessary, they will make appropriate recommendations for changes in protocol. [name] will conduct daily oversight of participant safety.

Any adverse events that are observed and/or reported will be immediately reported to [name]. Adverse event reporting will follow the MGB IRB's guidelines for reporting unanticipated problems, including adverse events. Reports of unanticipated problems and adverse events outlined in this policy that occur during the conduct of the study, after study completion, or after subject withdrawal or completion will be reported by the principal investigator, [name] within 5 working days/7 calendar days of the date she first becomes aware of the problem through Insight/eIRB. SAEs will also be reported in writing to the American Cancer Society. Adverse events will be reported to the Massachusetts General Hospital IRB and the American Cancer Society annually.

The PI will oversee the collection, maintenance, and analysis of all data. During weekly meetings with study staff and co-investigator, the PI will review the accuracy and completeness of the study questionnaires, consent forms, and app data. The study procedures and plans will also be reviewed during these meetings to ensure that they remain in line with the approved protocol.

To protect the privacy of each participant, we will assign a numeric study ID to each participant, which will be the primary identifier by which this person's progress through the trial will be reviewed. The database linking names and study identification numbers will be maintained in REDCap, which is password protected, and where access is limited to study staff, and access to study information is traceable. Only study staff will have access to this database. All staff are or will be fully trained in relevant ethical principles and procedures, including confidentiality. All assessment and treatment procedures will be closely supervised by the PI. All of the data will be captured electronically. For surveys and data entry by study staff, REDCap (Research Electronic Data Capture) will be used, which is a secure, web-based application designed to support data capture for research studies, and which is fully compliant with HIPAA-Security guidelines. The data generated by using our SiS app (i.e., app usage data)

will be kept on secure servers behind a firewall within the Partners network. The app will be hosted by secure ERIS/Partners servers. All data collected through the app will be transmitted using Transport Layer Security (TLS) encryption to prevent eavesdropping and tampering information while it is in the transmission pipeline.

